GDPR: For the data the Welsh Government requires, Welsh Government is the data controller and Aberystwyth University (WARU) is the data processor. For any other data, including sensitive personal data, the data controller and the data processor is Aberystwyth University (WARU).

167 mg capsule bottle containing the 2 capsules daily. The placebo will be matched to the active product by taste and texture.

60 capsules. Subjects will be asked to take

3.2) Quality

This product is free of the following components and their products thereof: cereals containing gluten, crustaceans, eggs, fish, peanuts, soybeans, milk (including lactose), nuts, celery, mustard, sesame seeds, sulphur dioxide and sulphite, lupin and molluscs, in compliance with Regulation (EC) No. 1169/2011. This product does not contain added colorants. Cultures are Kosher, Halah approved. The supplements are vegan, and they are produced and stored in a food grade facility. The freeze-dried culture is packaged inside waterproof and airproof pouches, consisting of three layers (in order, going inwards): polyester, aluminium, and polyethylene. The packaging material used is food grade.

3.3) Dose

The dose of investigational product and placebo will be 2 x 1 ml capsules daily.

4) Investigational Product Safety

The species *Lactobacillus paracasei* is included in EFSA's Quality Presumption of Safety (QPS) list. Total inactivated cells count > 1.5E+11 cells/g. The microbial strains are not genetically modified (GMO), in accordance to the European Directive 2001/18/EC. This product is not hazardous. Sacco S.r.l. is ISO 22000 and FSSC 22000 (food safety) certified since 2014. This product is considered safe with respect to bovine spongiform encephalopathy (BSE) or transmissible spongiform encephalopathies (TSEs) transmissions in accordance to Regulation EMA 410/01 rev. 3.

5) Study Design

5.1) Objectives of the Study

5.1.1) Primary Outcome Measure:

- Cognitive Control (Selective attention, processing speed, mental flexibility)

Cognitive Control (Selective attention, processing speed, mental flexibility) measured using the Stroop task in E-Prime

[Time Frame: Improved score (faster response time and improved accuracy) from baseline score at 6 weeks after pozibio]

- Cognitive Control (Selective attention, processing speed, mental flexibility)

Cognitive Control (Selective attention, processing speed, mental flexibility) measured using the Stroop task in E-Prime

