[Time Frame: Reduced Liver function test results at 6 weeks after pozibio when compared with placebo after 6 weeks]

➤ Changes in short chain fatty acids concentrations in plasma

Changes in short chain fatty acids concentrations in plasma measured using Gas Chromatography-Flame Ionization Detection

[Time Frame: Increased concentration of total short chain fatty acids after the pozibio at 6 weeks compared with the baseline]

➤ Changes in short chain fatty acids concentrations in plasma

Changes in short chain fatty acids concentrations in plasma measured using Gas Chromatography-Flame Ionization Detection

[Time Frame: Increased concentration of total short chain fatty acids after the pozibio at 6 weeks compared with that after placebo at 6 weeks]

5.2) Subject Selection

GDPR: For the data the Welsh Government requires, Welsh Government is the data controller and Aberystwyth University (WARU) is the data processor. For any other data, including sensitive personal data, the data controller and the data processor is Aberystwyth University (WARU).

- 30 participants, over 50

years, mixed gender, mixed ethnicity.

- **Inclusion Criteria:**

- Subjects over 50 years of age.
- Subjects with Mini-Mental State Exam (MMSE) of 25-30 inclusive (global cognitive function). Subjects who are able to undergo EEG and to commit to visits to WARU/P5.
- Subjects who are able to provide venous blood samples.
- Subjects able to provide written informed consent PRIOR to performing any study procedures.

- **Exclusion Criteria:**

- Subjects with diagnosis of Alzheimer's disease or other dementia.
- Subjects taking medication for the treatment of dementia (such as acetylcholinesterase inhibitors (Aricept, Exelon), memantine (Namenda) or other medications with similar mechanisms of action) or medical foods (such as Cerefolin, Souvenaid, Axona) for the treatment of dementia.
- Subjects who are already regularly taking probiotics, post-biotics, nutraceutical and/or vitamin supplements related to *PoZibio*™ within 30 days of screening.
- Subjects with Geriatric Depression Scale > 6.
- Subjects with a Mini Mental State Exam score below 25.
- Subjects who are pregnant or lactating.
- Subjects with medical condition or disease that is life threatening.
- Subjects who smoke cigarettes or use other products containing nicotine.
- Subjects diagnosed with diabetes.
- Subjects taking warfarin.

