- They are thanked for their time, and if they are happy to leave, then they are walked to the door.
- Their personal data is deleted in compliance with GDPR.

[figure not shown]
Testing day 1

Participants arrive at WARU on their pre-organised day and time after a 12 hour fast for a venous blood draw (3 tubes), followed by tea and toast. They are asked to complete an EQ-5D (5L) questionnaire. Their height and weight, waist, and hip circumference are measured. They are then free to leave, unless they have chosen to combine testing day 1 and 2 together, in which case they are guided to the P5 building where the activities outlined under testing day 2 commence.

Testing day 2 (can be combined with day 1 if needed)

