If participants opt not to combine testing days 1 and 2 together, then they are met at the main reception and guided to the P5 building, where they are encouraged to go to the toilet prior to testing. They are then taken to P4, where the EEG laboratory is located. They shall then undergo their first EEG and cognitive assessment. They are first asked to participate in an eyes open/closed task for measurements of their EEG resting state. Following this, three cognitive tasks (the Stroop task, the Go/No-go task, and the Flanker task) are digitally completed in a computer program called E-Prime. Practice rounds are provided for each task, with the researcher present, to allow for any questions before each experiment begins. After each task, the EEG program is stopped, and a new data file is created, before recording for the following task takes place. This provides an opportunity in between tasks for a sip of water, or a toilet break, if necessary, although the EEG cap must remain in place, and the nearest accessible toilets are in P5. Altogether, the tasks shall take approximately 60-70 minutes to complete, with an additional 45 minutes allocated for the application of the EEG cap. Participants are encouraged to bring their own bottled drinks, and snacks are made available. They are also granted access to the 'break out' room on the second floor of P5, prior to and following their participation, where there are chairs and tea/coffee machines available. Following their participation, participants are re-directed back to WARU for the collection of their capsules. Participants are reminded before taking part that they will not receive any scores post EEG testing, indicating how well they performed, but that the overall general findings of the study can be made available to them, following the end of the study, by contacting [contact].

Testing day 3

After the 6-week supplementation period, participants are asked to complete the activities that they undertook during testing day 2. A staff member is told to meet the participant in the P5 lobby to walk them over to P4. This is the final assessment of EEG and cognitive testing. If participants decide to combine testing days 3 and 4 together, then a staff member is made available to walk participants down to WARU.

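### Tea and coffee are available before the EEG and cognitive session, and the protocol text has no rule to standardise, match or record caffeine between testing days 2 and 3: a minor, cheaply removed source of noise

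*Protocol*

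**What the plan says.** The relevant text is in protocol section 5.3, read with the outcome list in section 5.1.1.

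- **Testing day 2** (baseline EEG, Stroop, Go/No-go, Flanker): participants may use a break-out room in the P5 building "prior to and following their participation, where there are chairs and tea/coffee machines available". They may also bring drinks, with no limit on content: "Participants are encouraged to bring their own bottled drinks, and snacks are made available".
- **Testing day 3** (week 6): "participants are asked to complete the activities that they undertook during testing day 2". Nothing is added on drinks, food or time of day.
- **Testing day 1**: participants attend "after a 12 hour fast for a venous blood draw (3 tubes), followed by tea and toast". They then leave, "unless they have chosen to combine testing day 1 and 2 together", in which case they go on to the EEG session.
- **Outcomes**: each measure from the session is listed twice as primary, once against baseline within the PoZibio arm (for Stroop, "Improved score (faster response time and improved accuracy) from baseline score at 6 weeks after pozibio") and once against placebo at 6 weeks.

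The protocol text available mentions no caffeine abstention period, no instruction to keep usual intake, no record of intake and no matching between the two EEG visits.

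**The concern.** The protocol fixes the conditions of the test day, and it fixes them so that tea or coffee may be taken before response time, accuracy, commission errors, P3/N2 components and alpha and delta activity are measured. A participant may have coffee before one EEG session and none before the other. If caffeine affects these measures, that difference becomes part of the participant's change from baseline and cannot be told apart from an effect of the product.

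Two kinds of comparison are exposed, in different ways. Against placebo, randomisation spreads caffeine intake over both arms, so the cost is lost precision. Against baseline within the PoZibio arm there is no such protection, so a difference between visits in the average caffeine state goes straight into the estimate. An SAP could not repair either, because intake is not recorded.

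**Working it through.** The protocol gives no effect size, SD, alpha or power, so there is no planned figure to reproduce. The following sizes the problem under stated assumptions.

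**Inputs from the protocol**
- 30 participants in total (section 2).
- Primary entries in section 5.1.1: Stroop 2, Go/No-go 2, Flanker 2, ERP 6 (three tasks, two each), alpha/delta 2, EQ-5D 2; total 16. From the EEG and cognitive session: 2 + 2 + 2 + 6 + 2 = 14. Half of these, 7, are against baseline within the PoZibio arm.

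**Assumptions (not in the protocol)**
- 15 per arm; the allocation ratio is not given.
- Caffeine shifts a measure by *d* = 0.3 to 0.5 SD of the quantity analysed.
- Each participant has had caffeine with probability *p* = 0.5 at each session.

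**1. PoZibio against placebo at week 6**

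Added variance = p(1 − p)d² = 0.25d².
- d = 0.3: 0.0225; standard error × √1.0225 = 1.011.
- d = 0.5: 0.0625; standard error × √1.0625 = 1.031.

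Without caffeine variation the standard error is √(2/15) = 0.365 SD, so it becomes 0.369 to 0.376 SD. In terms of sample size, 30 − 30/1.0225 = 0.7 and 30 − 30/1.0625 = 1.8, a loss equivalent to about one or two of the 30 participants.

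Chance imbalance between arms is already in that figure. The difference between arms in the proportion caffeinated has SD √(2 × 0.25/15) = 0.183, which shifts the contrast with SD 0.183d = 0.055 to 0.091. Adding its square to 0.365² gives √(0.1333 + 0.0030) = 0.369 and √(0.1333 + 0.0083) = 0.376, the same standard errors as above.

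**2. Change from baseline, precision**

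Let ρ be the within-person correlation of caffeine intake between the two sessions. Added variance of change = 2p(1 − p)(1 − ρ)d² = 0.5(1 − ρ)d².

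| | d = 0.3 | d = 0.5 |
|---|---|---|
| ρ = 0 (independent) | 4.5% | 12.5% |
| ρ = 0.6 (fairly stable habits) | 1.8% | 5.0% |

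**3. Change from baseline within the PoZibio arm, systematic shift**

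If the share of the arm that has had caffeine differs between visits by Δ, the mean change moves by s = dΔ. With n = 15 and pre-post correlation r of the outcome, the standard error is √(2(1 − r)/15): 0.258 at r = 0.5 and 0.200 at r = 0.7. The two-sided 5% false-positive rate (normal approximation) becomes Φ(s/SE − 1.96) + Φ(−s/SE − 1.96):

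| s (SD) | r = 0.5 | r = 0.7 | Δ needed at d = 0.5 | Δ needed at d = 0.3 |
|---|---|---|---|---|
| 0.1 | 6.7% | 7.9% | 0.20 | 0.33 |
| 0.2 | 12.1% | 17.0% | 0.40 | 0.67 |
| 0.3 | 21.3% | 32.3% | 0.60 | 1.00 |

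The last two columns (Δ = s/d) show how far the caffeinated share must differ between visits. The larger shifts need a large difference. With no average difference (Δ = 0), the rate stays at 5%.

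**The case against.** Several objections have force, and most of them limit the size of the point.

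- **Timing and place.** The text says the room is open before participation, not just before the tasks. The room is in P5, the EEG laboratory is in P4, and 45 minutes are allotted to fitting the cap. During the session the stated break is for water. This stands: one should not read the plan as serving coffee at the moment of testing.
- **The nicotine exclusion.** Section 5.2 excludes "Subjects who smoke cigarettes or use other products containing nicotine", and a reader might infer that the protocol contradicts itself by controlling one stimulant and supplying another. It does not. The criterion stands in a list beside diabetes and warfarin with no reason given, so no stimulant rationale can be attributed to it.
- **Bias between arms.** A reader might infer that chance imbalance in coffee drinking biases the comparison with placebo. It does not: under randomisation it is ordinary sampling error, already contained in the standard error.
- **Bias from the visit order.** When days 1 and 2 are combined, the tea comes before the baseline EEG. When days 3 and 4 are combined, the EEG is described first and the walk to WARU follows ("If participants decide to combine testing days 3 and 4 together, then a staff member is made available to walk participants down to WARU"). A reader might infer a built-in bias. The text shows a route by which caffeine state could differ between visits. It does not show that it will: combining is optional, the number who would combine is unknown, and other drinks are unrestricted at both visits.
- **Independence between visits.** Independent 50% intake is close to a worst case. Habits are likely to be similar at the two visits, which is why a correlation of 0.6 is also shown.
- **No source for the effect.** The protocol does not say that caffeine affects these measures. The range for *d* is assumed, and the cost falls to nothing as *d* approaches zero.
- **Instructions elsewhere.** Consent pages and a figure are absent from the copy reviewed, and appointment letters may carry such instructions. The claim is therefore limited to the protocol text available.

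What survives is that this text opens the machines before the primary measurements, and that nothing in it standardises, matches or records intake.

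**Conclusion.** The point holds as a minor, cheap improvement. Access to tea and coffee before the session, with no common instruction and no record, adds avoidable within-person noise to 14 of the 16 primary entries. For the comparisons with placebo at week 6 the cost is about 1% to 3% on the standard error, as noise and not as expected bias. For change scores it is 4.5% to 12.5% on the variance with independent intake, and about 2% to 5% at a within-person correlation of 0.6. These figures rest on an assumed effect of 0.3 to 0.5 SD and assumed 50% intake.

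The better reason to act is the seven from-baseline entries in the PoZibio arm. Randomisation does not protect them, and any average difference in caffeine state would pass straight into the estimate. The documents do not establish that such a difference will occur, nor its direction. The false-positive rates above therefore show what a given shift would do; they are not a forecast.

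**What to change.** In section 5.3 and the participant instructions:

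1. Open the tea/coffee machines only after testing. Before testing, offer water or decaffeinated drinks, and apply the same rule to drinks brought by participants and to the tea after the blood draw whenever the EEG follows on the same day.
2. Give one pre-test caffeine instruction, identical for testing days 2 and 3. For example, participants take their usual intake before arrival and repeat it at the same interval before testing at the second visit. A fixed abstention period would also serve, though habitual drinkers may find it less acceptable. What matters is that one rule is chosen and applied at both visits.
3. Record at both visits what caffeine was taken and when, so that departures can be seen and examined.

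The cost is a few lines of text, one short entry on the visit form and minor inconvenience to participants. No change to sample size, treatment or outcomes is needed.

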Note: All participants are encouraged to try to combine testing days 3 and 4 together (if possible), to ensure that cognitive testing and the venous blood draw occur within the same 48-hour window to when the last capsules of the 6-week trial are taken.

Testing day 4 (can be combined with day 3 if needed)

Within 48 hours after testing day 3, still following the supplementation regime, participants are invited to WARU after a 12 hour fast for their final venous blood draw (3 tubes), followed by tea and toast. They are then asked to digitally complete the EQ-5D (5L) and MMSE questionnaires. Their height and weight, waist, and hip circumference measurements are taken. There is an optional feedback questionnaire at the end.

6) Participant Risks

The supplements have already been tested for any adverse effects in a human cohort, however if any negative effects occur, participants are asked to refrain from continuing in the study.

EEG is non-invasive, however placing the EEG electrodes along the scalp can be time consuming (approximately 45 minutes), and participants are required to sit relatively still during the application and testing process (the application and testing process combined take approximately 2 hours). The application of the EEG cap requires EEG gel (saline solution) to be applied to the scalp, which makes hair messy upon removal of the cap. Participants are informed that towels will be placed along their shoulders to avoid the solution meeting their clothes, and these towels (in addition to paper towels) are provided to remove any excess gel from their hair. Participants are reminded that hair washing facilities are available in P5 for them to use, but that this would require a short walk from P4 back to P5. Therefore, participants are advised to bring a hat to cover their head for their own comfort. Participants are also reminded that venous blood draws can also cause localised soreness, stress, and dizziness.

7) Benefits to participant

There is no financial gain for participants if they decide to join this study. They will allow us to gain important insight into the PoZibio™ supplement to improve cognitive performance in healthy volunteers, which may be applied to other cohorts such as those suffering from vascular dementia and Alzheimer's disease.

8) Privacy/confidentiality

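### A combined baseline visit tests participants after food; a combined week-6 visit, as written, tests them before the fasting draw, so food state changes together with time point

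*Protocol*

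**What the plan says.** All the visit text is in Protocol 5.3, Study Design.

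**Combined baseline visit.** Testing day 1 brings participants to WARU "after a 12 hour fast for a venous blood draw (3 tubes), followed by tea and toast". The EQ-5D and body measurements follow. Those who combine days 1 and 2 then go on to testing, "in which case they are guided to the P5 building where the activities outlined under testing day 2 commence". Combining at baseline is offered if needed.

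**Combined week-6 visit.** Testing day 3 repeats the day 2 activities and starts at the other site: "A staff member is told to meet the participant in the P5 lobby to walk them over to P4". It continues: "If participants decide to combine testing days 3 and 4 together, then a staff member is made available to walk participants down to WARU". Testing day 4 is placed within 48 hours after day 3. It requires a 12-hour fast before the draw, with tea and toast afterwards. The note before it says "All participants are encouraged to try to combine testing days 3 and 4 together (if possible".

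**The EEG session.** Testing day 2 gives its length: "Altogether, the tasks shall take approximately 60-70 minutes to complete, with an additional 45 minutes allocated for the application of the EEG cap". On refreshments it says "Participants are encouraged to bring their own bottled drinks, and snacks are made available", and it gives access to a break room "prior to and following their participation, where there are chairs and tea/coffee machines available". No exception is made for a participant who still has a fasting draw to come, and no food state is set for any EEG session.

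**The concern.** Section 5.1.1 lists week 6 against baseline in the pozibio arm among the primary outcomes for every measure. If participants are tested fed at the first time point and fasted at the second, product and food state change together and that contrast cannot separate them. The direction is unknown, so the change could imitate a benefit or hide one.

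The alternative also costs something. A participant who takes up the snacks or the tea and coffee around the week-6 EEG session breaks the fast before the final draw. That affects fasting-dependent secondary outcomes in 5.1.2, such as triglyceride. It would be a departure from the stated fast, but one that the visit arrangements invite.

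**Working it through.** The plan gives no figure of its own on this point, so the check has four parts: visit order, timing, count of exposed entries, and an illustration of size.

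**1. Order**

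| Combined visit | Sequence as the text reads |
|---|---|
| Baseline (days 1 and 2) | 12 h fast, draw at WARU, tea and toast, EQ-5D and measurements, then EEG and tasks |
| Week 6 (days 3 and 4) | P5 lobby, EEG and tasks in P4, walk to WARU, draw after 12 h fast, tea and toast, EQ-5D |

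The baseline order is explicit. The week-6 order is inferred from three cues: the start in the P5 lobby, the walk down to WARU for those who combine, and day 4 being defined as after day 3. No text shown states the opposite. One figure before Testing day 1 is not shown.

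**2. Timing** (durations from Testing day 2)

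- Session length: 45 + 60 = 105 min to 45 + 70 = 115 min.
- Combined baseline: tasks start at least 45 min (cap application) after tea and toast, on the same visit.
- Combined week 6, fast exactly 12 h at the draw, walking time ignored: the session starts at 12 h minus 105 to 115 min = 10 h 05 to 10 h 15 of fasting. The tasks start at 12 h minus 60 to 70 min = 10 h 50 to 11 h.
- Combined week 6, fast already 12 h on arrival: tasks start at 12 h + 45 min = 12 h 45.

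**3. Primary entries exposed** (5.1.1)

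- 8 measures × 2 contrasts (against baseline, against placebo) = 16 entries.
- Against baseline: Stroop, Go/No-go, Flanker, ERP in each of the three tasks, alpha/delta activity, EQ-5D = 8.
- EQ-5D is listed after tea and toast at both times, so 8 − 1 = 7 are exposed.

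**4. Illustration of size**

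Only the total of 30 participants is from the protocol. Assumed: 15 in the pozibio arm, a two-sided 5% paired t-test, no product or practice effect, a shift δ (in SD of the score) in a share p of the arm, and retest correlation r. Then

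- SD of change = √(2(1 − r)), which is 1.000, 0.775 and 0.632 for r = 0.5, 0.7 and 0.8;
- noncentrality = √15 × pδ / √(2(1 − r)), on 14 degrees of freedom.

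Example: p = 1, δ = 0.2, r = 0.7 gives 3.873 × 0.2 / 0.775 = 1.00, and a rejection rate of 15.4%.

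Rejection rate in %, for δ = 0.2 / 0.3:

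| Share changing state | r = 0.5 | r = 0.7 | r = 0.8 |
|---|---|---|---|
| 20% | 5.2 / 5.5 | 5.4 / 5.9 | 5.6 / 6.4 |
| 30% | 5.5 / 6.2 | 5.9 / 7.0 | 6.4 / 8.1 |
| 60% | 7.2 / 10.0 | 8.7 / 13.4 | 10.5 / 17.7 |
| 80% | 8.9 / 14.0 | 11.6 / 20.1 | 15.0 / 27.8 |
| 100% | 11.2 / 19.2 | 15.4 / 28.7 | 20.8 / 40.2 |

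A simulation at r = 0.7 in which individuals either shift or do not (400,000 trials) agrees to within 0.4 percentage points.

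For smaller shifts at r = 0.7, δ = 0.1 gives 5.1% to 5.2% at a share of 20% to 30%, 5.9% to 6.6% at 60% to 80%, and 7.5% if all change state. δ = 0.05 gives at most 5.6%.

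For the between-arm test at week 6, with 15 per arm and a 0.3 SD shift in 20%, 30%, 60% or 80% of both arms, simulation (200,000 trials) gives 5.0%, 5.0%, 4.9% and 5.1%.

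**The case against.** The strongest reply is that this is an unspecified order for an optional visit format, not a contradiction. The text does not say when in the visit the walk to WARU happens, and the 48-hour wording most directly describes separate visits. The affected participants must combine at baseline, combine at week 6, keep the fast and decline the snacks, and no share is given. This stands as a limit. The text still points in one direction, and combining at week 6 is encouraged for everyone.

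No passage says that food state alters these tasks or EEG measures, and small shifts do little, as the 0.1 and 0.05 SD figures show. That also stands: the size is unknown.

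The comparison with baseline is weak anyway. A practice gain of 0.2 SD alone would give 15% rejection at correlation 0.7, and each exposed entry has a placebo-controlled counterpart. This is true, but practice affects this contrast whatever the visit order, whereas this confounder comes from the visit order.

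Re-ordering aligns only those who combine both times. Those who combine only at week 6 have no set food state at baseline, so whether theirs changes is unknown. This is correct, and it is why time since last meal should also be recorded.

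Finally, section 2 has both capsules taken with breakfast, and Testing day 4 says that the regime continues up to the final draw. A participant who eats breakfast before a combined week-6 visit is tested fed but has broken the fast. The conclusion therefore depends on the fast being kept, and these passages also need to be reconciled with the fasting draw.

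**Conclusion.** The concern holds. Followed as written, the visit order has participants who combine both times and keep the fast tested fed at baseline and fasted at week 6. For them, seven of the eight primary comparisons with baseline in the pozibio arm are confounded with food state. The effect on scores cannot be computed from the protocol. It ranges from negligible, if few combine both times or the shift is small, to a clear inflation of false positives if most of the arm changes state and the shift reaches 0.2 to 0.3 SD. Fixing the order would not bring this contrast to 5%, because practice effects remain. The randomised comparison at week 6 gains noise only. The conclusion rests on the natural reading of the week-6 text and on the fast being kept. It merits correction but does not threaten the randomised comparison.

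**What to change.** In 5.3, state one order for combined visits. At week 6 use the baseline order: fasting draw at WARU, tea and toast, then EEG and cognitive tasks. Say that no snacks, tea or coffee are offered before a fasting draw. Record time since last meal at every EEG session, so that food state is known for those who do not combine visits. Reconcile the capsules-with-breakfast wording in section 2 with the fast before the final draw.

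The cost is a short clarification and one recorded item, with the same staff, rooms and procedures. Both procedures stay on one day, so the 48-hour aim is kept. Booking at week 6 becomes slightly less flexible.

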If a participant, or a member of their family/household become unwell during the study, then they are pre-warned to alert a member of the research team immediately using the contact information they have been provided. Participation in the study will be suspended immediately until further discussion with the research team has taken place. If they become unwell at any point and need medical assistance, they are advised to contact 111 and seek advice from the NHS health sector or their doctor's surgery. We have a duty of care towards them and can help monitor their health remotely over 14 days and will help in any way we can.

- Data:

As above

10) Data analysis and statistics

EEG data analysis will be conducted at Aberystwyth University. Chemical composition using metabolomics will be conducted at AberInnovation and Aberystwyth University, and the quantification of short chain fatty acids as well as clinical biochemistry (Chem21 to include

Athrofa y Gwyddorau Biolegol, Amgylcheddol a Gwledig
Institute of Biological, Environmental and Rural Sciences

lipid panel tests) will be analysed
conducted by the Aberystwyth University researchers.

at Bronglais hospital. Statistics will be

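### Symptomatic adverse events are captured only when a participant reports them: no described visit asks, and no recording step is defined, so they cannot be reliably compared between arms

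*Protocol*

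**What the plan says.** - **Section 9, Safety Monitoring, participant part:** reports go to the study team: "If a participant, or a member of their family/household become unwell during the study, then they are pre-warned to alert a member". After such an alert, "Participation in the study will be suspended immediately until further discussion with the research team has taken place". The team also says it "can help monitor their health remotely over 14 days". The data part of section 9 only refers back to what stands above it.
- **Section 6, Participant Risks:** the protocol foresees possible negative effects of the supplement, and soreness, stress and dizziness from blood draws. On the supplement it says that "if any negative effects occur, participants are asked to refrain from continuing in the study". No recording of the effect is mentioned.
- **Section 5.3, Testing day 3:** "After the 6-week supplementation period, participants are asked to complete the activities that they undertook during testing day 2". That means resting EEG and the three cognitive tasks.
- **Section 5.3, Testing day 4:** fasting blood draw, body measurements and two questionnaires: "They are then asked to digitally complete the EQ-5D (5L) and MMSE questionnaires". Then: "There is an optional feedback questionnaire at the end". The content of that last form is not given.
- **Section 5.1:** liver tests, kidney tests and C-reactive protein (5.1.2) and EQ-5D-5L (5.1.1) are each to be compared with placebo at 6 weeks, all framed as expected benefits. For the liver tests, for example: "Reduced Liver function test results at 6 weeks after pozibio when compared with placebo after 6 weeks".

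**The concern.** Harms that participants feel but can tolerate do not obviously meet a trigger of being unwell. Someone with such symptoms could pass through the six weeks and the closing visits as described without being asked about them. What reaches the team would then be a selected set of volunteered reports, prompted by the same instruction that covers illness in the household.

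Two things are at stake. First, a low count of symptoms could reflect the absence of a question as much as the absence of symptoms. Second, the placebo arm, which could show which complaints are background, cannot serve that purpose unless both arms are asked in the same way. A later analysis plan cannot repair this, because it cannot recover events that were never elicited. How events are elicited belongs to the protocol.

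**Working it through.** The protocol states no adverse-event rate, safety sample size or reporting fraction, so there is no figure to reproduce. The main check is a reading of every contact in section 5.3 beside sections 6 and 9.

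| Contact | Described content | Asks about negative effects? |
|---|---|---|
| Pre-induction | MMSE, Geriatric Depression Scale, consent | No (before capsules) |
| Testing day 1 | Blood draw, EQ-5D-5L, body measurements | No (before capsules) |
| Testing day 2 | EEG, cognitive tasks, capsule collection | No (before capsules) |
| Six weeks of capsules | No scheduled contact described | No |
| Testing day 3 | EEG, cognitive tasks | No |
| Testing day 4 (within 48 hours of day 3, may be combined) | Blood draw, EQ-5D-5L, MMSE, body measurements, optional feedback form | Not described |
| After day 4 | No contact described | No |

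The remote monitoring over 14 days in section 9 is offered to those who have become unwell, so it does not replace asking everyone.

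**Illustration of what incomplete reporting does.** All inputs except the total of 30 (section 2) are assumptions: 1:1 allocation, so 30 / 2 = 15 per arm; the true rates; and a fraction d of events reported, equal in both arms.

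- Chance of at least one recorded event in an arm, true rate 10%: 1 − (1 − 0.10 × d)^15.
- Recorded difference for true rates of 40% and 10%: (0.40 − 0.10) × d.
- Power for that contrast: two-sided Fisher exact test at 5%, 15 per arm, with rates 0.40d and 0.10d.

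| d | At least one event recorded | Recorded difference (percentage points) | Exact power |
|---|---|---|---|
| 1.00 | 0.794 | 30 | 0.325 |
| 0.75 | 0.689 | 22.5 | 0.204 |
| 0.50 | 0.537 | 15 | 0.083 |
| 0.25 | 0.316 | 7.5 | 0.009 |

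The normal approximation gives higher power (0.473, 0.345, 0.231 and 0.130) with the same direction.

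**Consequences of a report.** Section 6 asks participants with negative effects not to continue. Section 9 suspends participation pending a discussion. The two overlap for a participant who feels unwell from the capsules, and they do not say the same thing.

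**The case against.** **The arms can be compared on some safety data.** A reader might infer that no safety comparison is possible. The documents do not support that. Liver and kidney tests, C-reactive protein and EQ-5D-5L (which includes pain/discomfort and anxiety/depression) are collected in both arms and compared with placebo. This stands, and it limits the point to symptomatic events. These data do not fill the gap: they do not record what happened, when, or whether capsules were interrupted. They may also be missing for people who stop early, since no early-stop visit is described.

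**The optional form is not the only closing form.** EQ-5D-5L and MMSE are also requested at testing day 4 and are not marked optional. This stands, but neither asks about adverse events.

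**Reactions to blood draws happen on site.** Immediate dizziness or soreness may be seen by staff without any later report. This is fair, but no step is described for recording it.

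**The trial is too small for safety conclusions anyway.** With 15 per arm, zero events would still allow a true rate of up to 1 − 0.05^(1/15) = 18% (one-sided 95% limit) or 1 − 0.025^(1/15) = 22% (two-sided). A reader might take these limits as the size of the defect. They are not: they follow from the sample size, hold under perfect elicitation and do not change with the fix. Likewise, exact power is only about 33% for 40% against 10% with full capture. So the fix cannot produce a strong comparison, only an interpretable count.

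**Reporting may not be discouraged.** One might infer that having to leave or pause deters reports. That is plausible, but the documents give no evidence for it, and the two sections differ on the consequence. The point does not rely on it.

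**Part of the record is not visible.** The content of the feedback form is not stated, and consent pages are not available. The finding is therefore that this protocol describes no question, not that nobody will ever ask one. No tolerability outcome is planned, which lowers the stakes.

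**Conclusion.** The point holds for symptomatic adverse events. As written, they are captured by spontaneous report alone, under a trigger shared with household illness, with no eliciting question at any described visit and no defined recording step. Under-recording is likely rather than certain, and a reliable between-arm comparison of symptoms is not available.

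The documents give no basis for its size. The illustrative figures rest on an assumed 15 per arm, assumed true rates and equal reporting in both arms. They show direction only. Unequal reporting could distort the contrast either way.

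This is a cheap and worthwhile improvement to a small supplement study without a safety endpoint. It does not threaten the cognitive outcomes.

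**What to change.** - **Ask everyone the same question.** At the week-6 assessment (testing day 3, or the combined day 3/4 visit), put one open question to every participant in both arms about any negative effects since starting the capsules. If day 4 is held separately, add only a brief update, since it falls within 48 hours of day 3.
- **Ask those who stop early.** Put the same question to anyone who leaves before week 6.
- **Record it.** Use a short form, separate from the optional feedback questionnaire, for what occurred, when, how severe it was and whether capsules were interrupted. Record household illness separately.
- **Report it.** Give counts by arm descriptively, and claim no tolerability from a low count.
- **Reconcile sections 6 and 9** on what follows a report. Which consequence applies is for the investigators to settle.

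Cost: a few minutes per participant at existing visits, plus a short contact for early stoppers. More minor complaints will be recorded in both arms. The answer also relies on recall over six weeks, so mild or early symptoms may still be missed.
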